#### **4.2. Scientific Rationale for the Study Design**

This *Proof of Concept* study is designed as a multiple-arm trial with three arms of CPL409116 in different dose and one placebo arm. Since the primary goal of the study is to provide an early evidence of anti-inflammatory effect of CPL409116 in rheumatoid arthritis by influence on downstream proteins' phosphorylation as a consequence of JAK/ ROCK inhibition, it is to include placebo arm as the control and investigational drug arm to document clinical benefits. There exist definable conditions that should be fulfilled before placebo-controlled trials is to be proceed. The assessment of these clinical conditions is grounded in the ethical requirements and reflects the current guidance of the OPRR guidelines. For the approval of placebo controls in phase 2 trials some aspects should be considered. First of all rheumatoid arthritis is the well-known disease for which treatment is available however access to some of therapies can be limited (the biologic treatment accessible in therapeutic programs only, injection/ infusion as a route of delivery) and some of them show ineffectiveness in reduction of pathologic changes in joints or do not bring relief in pain. In this placebo-controlled study patients are to administer methotrexate (according to current guidelines MTX is recommended as a first-line RA treatment) which do not bring anticipated effects. During the treatment period patients will be taking painkillers if needed (paracetamol) which should be ceased 24h before an ambulatory visit. Corticosteroids, opioids (tramadol) and NSAIDs are to be continued without change of dosage and route of administration through appropriate period of time before Day 1 of the study in order to avoid any impact of mentioned above drugs on evaluation of IMP effectiveness. The main purpose of this *Proof of Concept* trial is to demonstrate benefits from the JAK/ ROCK inhibitor administration in patients with RA who are treated ineffectively and need new therapeutic options which will be able to improve their quality of life. Nowadays JAK inhibitors are registered, accessible and applied in the treatment of patients with RA, e.g. tofacitinib, hence this mechanism of action is confirmed as an effective solution in autoimmunity. CPL409116 has a dual mechanism of action (JAK inhibition and Rho-associated kinases inhibition) therefore this controlled placebo trial can be the prelude to achieve promising results not only in patients with RA but at the same time in patients with RA complicated by other concomitant diseases.

Doses of CPL409116 which were chosen to phase II of the study had been confirmed as safe and well-tolerated in PART B. Duration of the study equals 12 weeks (3 months) was indicated on the basis of preclinical studies conducted with CPL409116 in rodents (rats) and non- rodents (dogs). It seems to be the sufficient period of time to show effectiveness and tolerance of the investigational product.

### 4.3. Justification for Dose

A series of nine horizontal black bars of varying lengths, decreasing in size from top to bottom. The bars are evenly spaced and extend across the width of the frame.

#### 4.4. Study Duration

The duration of participation for each patient will be approximately up to 20 weeks. The estimated study duration includes:

- The Screening Period: up to 28 days
- Treatment period: Day 1 to 85/86 days
- Follow-up period: patients are to come to the study centre two times after the last dose of IMP: at Week 14 and Week 16 (Day 99 and Day 113 respectively). On Day 92 and Day 106 the call from the study unit will be made. End of the Study will take place on Day 113, Week 16.

For the entire study, end of the study is defined as the last visit of the last subject for any protocol related activity (last subject, last visit- LSLV).

## 4.5. Study Completion

A subject is to be considered to have completed the double-blind treatment phase if he/she has completed all the assessments and procedures on Day 113. A subject who, for any reason, discontinues the study before Day 113 will not be considered to have completed the study.

## 4.6. Early Termination

If a subject withdraws prematurely after dosing, all data normally collected at discharge from the clinical center should be collected at the time of premature discontinuation or at the scheduled discharge. Patients that withdraw or are withdrawn from the study will attend an early termination visit at the study unit and 2 safety Follow-up visits after the last dose of IMP.

## 5. STUDY POPULATION

Male and female patients with a diagnosis of with moderate-severe active rheumatoid arthritis (RA) who have had an inadequate response to methotrexate (MTX).

Subjects must complete all screening procedures and assessments and have test results available prior to the baseline visit (Visit 2). If patient's status after Screening changes at Baseline (Day 1) and the patient no longer meets all eligibility criteria, the patient should be excluded from participation in the study (such patient is to be considered as a screen failure).

### 5.1. Number of Subjects

A total of 100 patients will be enrolled in the Study.

### 5.2. Inclusion Criteria:

**Patients eligible for inclusion in this study have to fulfil all of the following criteria:**

- 1) Age  $\geq 18$  and  $\leq 75$  years at the time of signing informed consent.
- 2) Meets ACR/EULAR 2010 RA Classification Criteria with a duration of RA disease of  $\geq 6$  months at time of screening and participant not diagnosed before 16 years of age.
- 3) Must have active disease at both screening and baseline, as defined by having all three listed below:
  - a)  $\geq 6/68$  tender/painful joints (TJC),
  - b)  $\geq 6/66$  swollen joints (SJC).
  - c) DAS28  $> 3,2$

**NOTE:** If surgical treatment of a joint has been performed, that joint cannot be counted in the TJC or SJC for enrolment purposes.

- 4) Must have a C-reactive protein (CRP) measurement  $\geq 7$  mg/L at screening.

**NOTE:** If patient's CRP level is below 7 mg/L on Screening visit, it is possible to perform CRP measurement once again within 28 days of Screening period, provided at least 14 days since initial CRP measurement and prior to Day -5 before Baseline.

- 5) Must meet Class I, II or III of the ACR 1991 Revised Criteria for Global Functional Status in RA.
- 6) Must have inadequate response, despite currently taking Methotrexate (MTX): weekly 15-25 mg oral or injected (subcutaneous or intramuscular) for at least 12 weeks prior to Screening, and with no change in dosage and route of administration for at least 8 weeks prior to Day 1/ baseline. A lower dose of  $\geq 10$  mg/week is acceptable if reduced for reasons of side effects or intolerance to MTX, e.g.

nausea/vomiting, hepatic or hematologic toxicity (there must be clear documentation in the medical record).

- 7) If using oral GCS must be on stable dose (equivalent to  $\leq 10$ mg/day of prednisone) for at least 4 weeks prior to Day 1/ baseline.
- 8) If using NSAIDs must be on stable dose for at least 4 weeks prior to Day 1/ baseline.
- 9) A woman must be either:
  - a) Not of childbearing potential:
    - postmenopausal: **>45 years** of age with spontaneous amenorrhea for **at least 12 months**. In addition, in women **under the age of 60 years** postmenopausal status must be confirmed with **FSH level  $\geq 40$  IU/L** at screening, without using hormone replacement therapy (women treated with hormone replacement therapy require a wash-out period in order to obtain physiologic FSH level; the duration of the wash-out depends on the type of hormone replacement therapy and the Investigators should use their judgment in determining the wash-out period);
    - permanently sterile (hysterectomy, bilateral salpingectomy; bilateral oophorectomy); or otherwise be incapable of pregnancy.

**NOTE:** premenopausal women who have had a bilateral tubal ligation/occlusion are considered capable of becoming pregnant.

- b) Of childbearing potential and **using a double contraception** including a barrier method (condom or occlusive cap) and a highly effective method of birth control (listed below):

**NOTE:** highly effective methods of contraception are defined as:

- established use (i.e. at least 8 weeks prior to Day 1) of combined (estrogen and progesterone) hormonal contraception associated with inhibition of ovulation (oral, intravaginal, transdermal, injectable) or progesterone-only hormone contraception associated with inhibition of ovulation (oral, injectable);
- intrauterine device (IUD) or intrauterine hormone-releasing system (IUS);
- bilateral tubal occlusion/ligation;
- vasectomized partner (vasectomized partner should be the sole partner for that subject and the absence of sperm should be confirmed).

**NOTE:** sexual abstinence, defined as refraining from heterosexual intercourse throughout the study and for 12 weeks after the last IMP dose, is acceptable as a sole contraception method when this is in line with the preferred and usual lifestyle of the subject.

10) Participant (**a man**) who is sexually active with a woman of childbearing potential must agree **to use a double contraception** including a barrier method (male condom) and a highly effective method of contraception (highly effective method of contraception are listed above) during the study and 12 weeks after the last dose of CPL409116/ placebo administration.

**NOTE:** Male subjects are responsible for informing his partner(s) of the risk of becoming pregnant and for reporting any pregnancy to the study doctor.

**NOTE:** Participants (males and females) are furthermore willing to use contraception methods for 12 weeks after the last dose of CPL409116/ placebo administration. It is crucial to maintain appropriate methods of contraception if it is planned to continue methotrexate administration after the end of the study.

11) A woman of childbearing potential must have a negative blood pregnancy test ( $\beta$ -human chorionic gonadotropin [ $\beta$ -hCG]) at screening and negative urine pregnancy test on Day1/ baseline.

12) Informed Consent Form signed and dated prior to Screening evaluations.

13) Ability and willingness to comply with the requirements of the study Protocol.

14) Negative result of the COVID-19 RT-PCR test (real-time reverse transcription polymerase chain reaction) for the qualitative detection of nucleic acid coming from SARS- CoV-2 before inclusion to the study (Screening- 72 h before Day1/ baseline).

### 5.3. Exclusion Criteria

**Patients eligible for inclusion in this study must not fulfill any of the following criteria:**

- 1) Has had a serious infection (e.g. sepsis, pneumonia, pyelonephritis or any other serious infection as per Investigator's judgement), or has been hospitalized or received intravenous antibiotics for an infection within 3 months prior to Day 1/ baseline.
- 2) Any active infection including localized infections within 2 weeks prior to baseline.
- 3) History of opportunistic or recurrent (3 or more of the same infection requiring anti-infective treatment in any rolling 12-month period) infection.
- 4) History of chronic infections requiring anti-infective treatment within 6 months prior to Screening.
- 5) Subjects with a high risk of infection in the Investigator's opinion (e.g. subjects with leg ulcers, indwelling urinary catheter).
- 6) History of infected joint prosthesis or other implanted device with the retention of prosthesis or device in situ.
- 7) Symptomatic herpes zoster within 3 months prior to Screening.

- 8) History of disseminated herpes simplex infection or disseminated/complicated herpes zoster.
- 9) Hereditary or acquired immunodeficiency disorder, including immunoglobulin deficiency.
- 10) Known infection with human immunodeficiency virus (HIV) or positive test at Screening.
- 11) Presence of any of the following laboratory abnormalities at Screening:
  - a) Alanine aminotransferase (ALT) or aspartate aminotransferase (AST) levels 1.5 x the upper limit of normal (ULN);
  - b) Absolute neutrophil count of  $<1.5 \times 10^9/\text{L}$  ( $<1500/\text{mm}^3$ );
  - c) Absolute lymphocyte count of  $<0.75 \times 10^9/\text{L}$  ( $<750/\text{mm}^3$ );
  - d) Absolute white blood cell (WBC) count of  $< 3.0 \times 10^9/\text{L}$  ( $<3000/\text{mm}^3$ );
  - e) Hemoglobin  $<9.0 \text{ g/dL}$  ( $90 \text{ g/L}$ );
  - f) Thrombocytopenia, as defined by a platelet count  $<100 \times 10^9/\text{L}$  ( $< 100\,000/\text{mm}^3$ ) at Screening;
  - g) Total bilirubin  $\geq 1,5 \times$  the upper limit of normal (ULN).
- 12) Current or history of clinically significant (per Investigator's judgment) liver or biliary disease or significantly abnormal liver function test at screening (ALT or AST level  $\geq 1.5 \times$  ULN and/or total bilirubin  $\geq 1,5 \times$  the upper limit of normal (ULN)).
- 13) Current acute or chronic HCV and/or HBV infection:
  - a) subjects who are seropositive for antibodies to hepatitis C virus (at Screening) may be allowed to participate in the study provided they have 2 negative HCV RNA test results 6 months apart after completing antiviral treatment and prior to Screening, and have a third negative HCV RNA test result at Screening.
  - b) HBV serology:
    - a positive result for HBsAg will be exclusionary;
    - a positive result for anti-HBc antibodies in subjects negative for HBsAg requires HBV DNA testing. A positive test result for HBV DNA will be exclusionary;
    - for subjects who are negative for HBsAg and anti-HBc antibodies and has had a HBV vaccination a positive test result for anti-HBs antibodies is expected – such subjects may be enrolled without HBV DNA testing. In non-vaccinated patients positive for anti-HBs antibodies HBV DNA testing is required;
    - a positive result for HBV DNA will be exclusionary.

**NOTE:** enrolled subjects positive for anti-HBc antibodies and/or anti-HBs antibodies (except for vaccinated subjects negative for anti-HBc antibodies and positive for anti-HBs antibodies) **will have repeated HBV DNA testing at week 6** (or early termination visit) and last follow-up visit. A positive result for HBV DNA testing in these subjects will require immediate interruption of study drug and a hepatologist consultation.

- 14) Current or history of clinically significant renal disease (per investigation judgment) or eGFR<60mL/min/1.73m^2.
- 15) Breast cancer or other malignancy (including lymphoma, leukemia) within the past 5 years except for cervical carcinoma in situ that has been completely resected with no evidence of recurrence or metastatic disease for at least 12 months or cured basal cell carcinoma with no evidence of recurrence for at least 12 months.
- 16) History of major organ transplant (e.g. kidney, heart, liver, lung) or hematopoietic stem cell/bone marrow transplant.
- 17) History of lymphoproliferative disease or signs/ symptoms suggestive of possible lymphoproliferative disease, including splenomegaly or lymphadenopathy.
- 18) History of or current moderate to severe congestive heart failure (New York Heart Association [NYHA] class III or IV), or within the last 6 months, a cerebrovascular accident, myocardial infarction, unstable angina, unstable arrhythmia or any other cardiovascular condition which, in the opinion of the investigator, would put the subject at risk by participation in the study.
- 19) History or presence of other significant concomitant illness that, according to the Investigator's judgment, would place the participant at unacceptable risk when taking investigational product or could interfere with the interpretation of data.
- 20) History of other (than RA) chronic inflammatory arthritis or systemic autoimmune disorder other than Sjögren's syndrome secondary to RA, that may confound the evaluation of the effect of the study intervention such as mixed connective tissue disease, psoriatic arthritis, juvenile chronic arthritis, spondyloarthritis, Felty's Syndrome, systemic lupus erythematosus, scleroderma, Crohn's disease, ulcerative colitis, or vasculitis.
- 21) Presence of fibromyalgia that, in the Investigator's opinion, would make it difficult to appropriately assess RA activity for the purposes of this study.
- 22) Undergone any major surgery within 8 weeks prior to study entry or will require major surgery during the study that, in the opinion of the Investigator would pose an unacceptable risk to the participant.
- 23) Current or previous active *Mycobacterium tuberculosis* (TB) regardless of treatment.

- 24) Evidence of latent TB (as documented by a positive QuantiFERON-TB test at Screening, no findings on medical history or clinical examination consistent with active TB, and a normal chest radiograph).
- 25) Previous household contact with a person with active tuberculosis (TB) and did not receive appropriate and documented prophylaxis for TB.
- 26) Clinically significant multiple or severe drug allergies or severe post-treatment hypersensitivity reactions (including, but not limited to, erythema multiforme major, linear immunoglobulin A dermatosis, toxic epidermal necrolysis, and exfoliative dermatitis).
- 27) Inherited or acquired thrombophilia and/ or current or history of thromboembolic events/ disease.
- 28) Screening 12-lead ECG that demonstrates relevant abnormalities that, in the opinion of the Investigator, are clinically significant and indicate an unacceptable risk for the subject's participation in the study (eg, QTc >450 msec or a QRS interval >120 msec). If QTc exceeds 450 msec, or QRS exceeds 120 msec, the ECG should be repeated two more times and the average of the three QTc or QRS values should be used to determine the subject's eligibility.
- 29) Pregnancy or breast- feeding.

**NOTE:** Women of childbearing potential must have a negative pregnancy test at Screening, at randomization and at scheduled visits throughout the study.

- 30) Narcotic and alcohol addiction or abuse (more than 14 alcohol units per week: one unit = 150 mL wine, 360 mL beer, 45 mL 40 % spirits) (UK guidelines).
- 31) Positive drug screen or alcohol breath tests.
- 32) Blood donation within the last month before Day1/ baseline.
- 33) Current therapy with any disease-modifying antirheumatic drug (DMARD) other than MTX. All DMARDs (except for MTX) must be ceased before Day 1/ baseline, as follows:
  - **1 month before:** etanercept, sulfasalazine, chloroquine/ hydroxychloroquine;
  - **3 months before:** leflunomide (4 weeks in case of cholestyramine washout);
  - **3 months before:** adalimumab, golimumab, infliximab, certolizumab, tocilizumab, gold, cyclosporine, penicillamine, azathioprine.

**NOTE:** For biological agent, previous use of one (and only one) treatment listed above (tocilizumab or TNF-alpha inhibitor) is allowed, if administered for less than 3 months or ceased because of other than lack of effectiveness causes.

- 34) Previous use of:
  - a) Cyclophosphamide
  - b) Tacrolimus

- 35) Previous use of JAK inhibitors.
- 36) Previous use of biologic agent other than tocilizumab or TNF-alpha inhibitor except for biologic agents that were considered as DMARDs and used as an investigational medicinal product within a clinical trial if a 30 days or 5 half-lives (whichever is longer) washout period was applied.
- 37) Vaccinated with a live vaccine (i.e. containing live or attenuated pathogens) within 3 months before Day 1/ baseline or necessity to vaccinate during the clinical trial.

**NOTE:** Investigators should ensure that all study enrolment criteria have been met at Screening and on Day 1. If a patient status after Screening changes at baseline (Day 1) such that the study patient no longer meets all eligibility criteria, then the patient should be excluded from participation in the study (such patient is to be considered as screen failure). History or presence of any other medical or psychiatric condition, or laboratory abnormality that, in the opinion of the Investigator, may place the subject at unacceptable risk for study participation or may interfere with the study results should be considered as an exclusion criterion.

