
Blood samples collection
	
Blood samples for laboratory tests
 
Blood Chemistry, Hematology, Coagulation are to be collected:
 

once during the Screening period and next on Day 1/ Baseline, 8, 29, 57, 85 – as a treatment period and on Day 99 and 113 during the Follow-up period.

 
Blood samples to evaluate:
 

Rheumatoid Factor (RF) are to be collected during the Screening, at Baseline/ Day 1 (Visit 2), Week 1 (Day 8), Week 4 (Day 29) Week 8 (Day 57), Week 12 (Day 85), on Day 99 and 113 during the Follow-up period and in case of early withdrawal;

C-Reactive Protein (CRP), Erythrocyte Sedimentation Rate (ESR) are to be tested during the Screening, Baseline/ Day 1, Week 1, Week 4, Week 8, Week 12, Week 14 and Week 16 and in case of early withdrawal;

Anti CCP Antibodies (ACPA) are to be collected during the Screening, at Baseline/ Day1, Week 4 (Day 29) Week 8 (Day 57), Week 12 (Day 85), Day 113 and in case of early withdrawal.

 
Fasting lipid profile: fasting total cholesterol, LDL, HDL, triglycerides will be assessed at Screening, at Baseline/ Day1, Week 1 (Day 8), Week 4 (Day 29) Week 8 (Day 57), Week 12 (Day 85), on Day 99 and 113 during the Follow-up period and in case of early withdrawal (samples must be collected after a minimum 6-hour fasting).
 
QuantiFERON sampling: Test is to be performed at Screening.
 
HBsAg, HbcAb, HBsAb, HBV DNA, HCVAb, HCV RNA; HIV tests are to be performed at Screening.
 
Total blood loss regarding tests listed above in the study is to be approximately ca 230 mL per each subject.
 
PK sampling Blood samples for PK analysis are to be collected on the following Days: 1/Baseline; 8; 57 (timepoints: pre-dose and 0.5; 1.0; 1.5; 2.0; 2.5; 3.0; 4.0; 6.0h after CPL409116 administration in the morning) and on Day 29 in the following timepoints: pre-dose (0.0) and 2.5h after CPL409116 administration

	
in the morning.
 
On Day 85 PK blood sample collection is to be carried out in 13 timepoints, as follows: pre-dose (0.0) and 0.5; 1.0; 1.5; 2.0; 2.5; 3.0; 4.0; 6.0; 8.0; 10; 12; 24h (Day 86) after CPL409116 administration in the morning.
 
Per each sample will be taken 4,5 mL of blood.
 
Total amount of blood for PK tests during the study is to be equal approx. 189 mL.
 

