## **9. STUDY SCHEDULE**

**The study is to include 3 phases:**

- A Screening phase of up to 4 weeks;

- A double-blind treatment phase (Day 1 to Day 85/86; 12 weeks) with two IMP administrations per day in the morning and in the evening (except Day 85 with CPL409116 administration in the morning only, and except Day 86 without CPL409116 administration and with donation of the last sample of blood for PK analysis). Ambulatory visits will take place on Day 1, 8, 29, 57 and 85/86. Phone calls will be made on Day 15, 22, 43 and 71.
- A 4 weeks post-treatment follow-up phase up to Week 16 (Day 113). Patients are to come to the study centre two times after the last dose of IMP. Every week (for 4 weeks after the last IMP administration) there is to be contact with patients: an ambulatory visit or phone call from clinical centres: Week 14 and 16 (Day 99 and 113 respectively)- an ambulatory visit; Week 13 and 15 (Day 92 and 106 respectively)- phone call from a clinical centre. The end of the study is planned at Week 16 (Day 113).

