### **Administration of CPL409116 or placebo;**

- Collect blood samples to the PK analysis 2.5h (+/- 5 min) after CPL409116 administration;

- Review of the diary for compliance with daily diary completion (and provide subject retraining as required);
- Dispense subject a part of the diary, where they can record daily study medications (including new, stopped and changes in medications in addition to the study medication) they are taking during the study treatment;
- Dispense investigational products;
- Collect used blisters;
- Serious and non-serious adverse events monitoring.

## Phone call visit, Day 43/Week 6

Phone call is to be made in order to:

- remind a subject about the ambulatory visit taking below listed aspects into account:
  - conditions (e.g. fasting condition)
  - IMP and used blisters
  - filling out the diary.
- Interview of the Subject's condition:
- symptoms of potential presence of viral or bacterial infection (e.g. body temperature, symptoms such as cough, dyspnea, sore throat and others, Questionnaire regarding possible SARS-CoV-2 infection);

All phone call visits need to include:

- collecting data about adverse events, concomitant medications, interview of the Subject's overall condition and any other questions, on the Investigator's discretion.

## Visit 6, Day 57/Week 8

Patients are required to be fasted for at least 6 hours prior to the visit. The following assessments should be done before other study related procedures and before significant contact with the principal investigator and site personnel:

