**Procedures that will be performed on Visit 10, Day 113/Week 16 include:**

- ACR/DAS Assessments: Tender/Painful Joint Counts (68), Swollen Joint Count (66), Patient's Assessment of Arthritis Pain, Patient's Global Assessment of Arthritis, Physician's Global Assessment of Arthritis, Health Assessment Questionnaire –Disability Index (HAQ-DI); SF-36 RAND; FACIT-fatigue scale;
- Questionnaire regarding possible SARS-CoV-2 infection;
- Review concomitant Medication and Treatments (RA and non RA): Current and prior medications (noting exclusions and required DMARD restrictions) taken with reasons and should include dose/duration;
- Vital signs: sitting blood pressure, pulse, and temperature;
- Perform complete physical Examination;
- 12-lead electrocardiogram;
- Collect blood samples for chemistry, haematology and coagulology laboratory assessments;
- Collect blood sample for ACPA, CRP, RF, ESR and lipid profile assessment;
- Collect urine sample for laboratory urinalysis and urine microscopy;
- Collect urine for urine pregnancy testing (women of childbearing potential, only);
- Confirm proper contraception is being used;
- Collect urine sample for toxicology tests (presence of drugs in urine), alcohol breath test;
- Serious and non-serious adverse events monitoring;
- Register the subject's status as completed and discharge the subject from the study.

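### The Week 6 repeat HBV DNA test is assigned to a phone call and can be missed, although for patients who complete treatment it is the only repeat that could lead to interruption of study drug.

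*Protocol*

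**What the plan says.** **The requirement.** The note to criterion 13 (protocol section 5.3) covers enrolled patients positive for anti-HBc and/or anti-HBs antibodies, except vaccinated patients who are anti-HBc negative. They "will have repeated HBV DNA testing at week 6", with the remaining occasions given as "or early termination visit) and last follow-up visit". The consequence is explicit: "A positive result for HBV DNA testing in these subjects will require immediate interruption of study drug and a hepatologist consultation". The synopsis copy of criterion 13 and footnote u to Table 1 repeat the rule. The SAP copies it in section 2.2.1 and in its own Table 1.

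**The schedule table.** The hepatitis row of protocol Table 1 has a plain mark at Screening, a bracketed mark at Week 6, and a second bracketed mark in one of the last columns.

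**The contacts.** Section 9 states "Ambulatory visits will take place on Day 1, 8, 29, 57 and 85/86" and "Phone calls will be made on Day 15, 22, 43 and 71". The synopsis study design and section 4.1 also make Day 43 a phone call. The section 9.2 entry is headed "Phone call visit, Day 43/Week 6". It lists reminders, a symptom interview, adverse events and concomitant medication, and no sample.

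**The visit lists.** The Day 113 list in section 9.3 has chemistry, haematology and coagulation, and then "Collect blood sample for ACPA, CRP, RF, ESR and lipid profile assessment". The early withdrawal list in section 9.4 is similar. Neither names HBV DNA. The only list in section 9 that does is Screening (section 9.1), which is the entry test and not the repeat.

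**The concern.** The protocol ties a mandatory action on study drug to a blood result, and then assigns that blood test to a contact at which no blood is taken. Staff who prepare a visit from section 9 find no prompt for the sample at Week 6, Day 113 or early withdrawal.

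At stake is a patient safeguard. Section 2.7 itself describes participants as receiving two immunosuppressive agents. If the Week 6 sample is not taken, a flagged patient can go through the whole treatment period without the check that the protocol set for that period.

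**Working it through.** The plan states no figure to reproduce. The check compares the sections and does day arithmetic.

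**1. Is there a clinic visit at Week 6?**
- Week 6 is Day 6 × 7 + 1 = 43. The Table 1 window of ±2 days gives Days 41 to 45.
- Clinic visits during treatment are on Days 1, 8, 29, 57 and 85/86. The nearest are 43 − 29 = 14 days before and 57 − 43 = 14 days after.
- With both windows stretched to the limit, a Day 29 visit on Day 31 and a Day 57 visit on Day 55 still leave gaps of 41 − 31 = 10 and 55 − 45 = 10 days.
- No planned clinic visit can therefore fall inside the Week 6 window.

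**2. Does another procedure bring the patient in on Day 43?** The Table 1 footnotes for vital signs, chemistry and haematology, urinalysis, PK sampling and product dispensing list their days. None names Day 43.

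**3. Do the section 9 lists carry the sample?**

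| Required occasion | Contact in section 9 | HBV DNA in its list? |
|---|---|---|
| Week 6 (Day 43) | Phone call, section 9.2 | No |
| Early termination (alternative to Week 6) | Clinic visit, section 9.4 | No |
| Last follow-up visit (Day 113) | Clinic visit, section 9.3 | No |

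This counts list entries. It does not forecast how many tests will be missed.

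**4. Which result could lead to interruption of study drug?**
- The last dose is on the morning of Day 85, and Day 113 is 113 − 85 = 28 days later. A positive result then can still lead to the hepatologist consultation, but no study drug is left to interrupt.
- Under section 7.2 a patient who stops treatment leaves the trial, so an early termination sample comes when dosing is already ending.
- At Day 43, 85 − 43 = 42 days remain to the last dose. For a patient who completes treatment, this is the only repeat test whose result could trigger the interruption. It is also the one assigned to a phone call.

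**5. What cannot be settled.** The text available to me does not show whether the second bracketed mark in the hepatitis row belongs to Week 16 or to early withdrawal. Nothing above depends on it.

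**The case against.** The strongest reply is that the test is in the schedule. Table 1 marks it at Week 6, the brackets fit a test for a subgroup, and footnote u defines that subgroup. Sections 8 and 8.2 send the timing of assessments and laboratory samples to Table 1, so a site working from section 9 alone would not be following the whole protocol. Section 1.3 allows unplanned visits where evaluations are needed to protect a patient. Flagged patients also need a negative HBV DNA result to enter, and chemistry including ALT and AST continues at Days 8, 29, 57, 85, 99 and 113.

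Much of this stands, and it limits the point. A reader might infer that sites would never draw the sample, or that none of the required tests would be done. The documents do not support that: criterion 13, Table 1 and footnote u all call for the test, and a site that reads them can arrange an extra attendance.

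A reader might also infer that the synopsis confines hepatitis testing to Screening, because its sampling paragraph ends "HIV tests are to be performed at Screening". That does not follow either. The sentence does not say only, it can be read as the panel done in every patient, and the same synopsis repeats the Week 6 rule under criterion 13.

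The contradiction itself remains. The Week 6 mark sits in a column that four other places define as a phone call. Section 8.2 settles the timing of the sample but provides no contact at which to take it. Unplanned visits depend on the Principal Investigator, and nothing in the Day 43 entry prompts one. Routine chemistry is not the trigger that the protocol names.

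**Conclusion.** The point holds as an internal inconsistency that affects patient safety. It does not challenge a design choice, and no endpoint, estimate or efficacy analysis depends on it. A required on-treatment test is scheduled for a contact without sampling, and none of the three matching section 9 entries names the sample. The supported conclusion is that the test can be missed, not that it will be.

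The group affected is every enrolled patient with the flagged serology. The documents give neither their number nor their share of the planned 100, so no count of missed tests can be offered. For each such patient who completes treatment, one test is at stake: the only repeat that could lead to the required interruption.

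The conclusion assumes that the Week 6 mark is placed as it appears in Table 1, which criterion 13 and footnote u confirm. It also assumes that no site document outside the protocol and SAP already arranges the sample.

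**What to change.** Reconcile criterion 13 (section 5.3 and the synopsis), Table 1 with footnote u, the Day 43 statements in the synopsis study design and sections 4.1, 9 and 9.2, the Visit 10 list in section 9.3, and the early withdrawal list in section 9.4. All should name the same timepoints and an on-site contact at which this sample can be drawn. Add the sample, marked as conditional on the flagged serology, to each matching procedure list. Carry the result into the SAP's copy of the criteria and schedule. Which visits are right is for the sponsor to decide.

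The cost is protocol wording and, for flagged patients only, possibly one extra on-site attendance for a test that is already required.
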